Benefits to human subjects. All participants will have access to training in skills that could be useful in obtaining employment. Training may be provided in typing, keypad, general computer use, reading, math, GED preparation, the use of Microsoft computer applications. IPS supported employment will be provided to help participants become employed. Since all participants in this study will be unemployed at the start of the study, this experience could help prepare participants for employment.

All participants will receive monetary incentives for attending the Therapeutic Workplace during the first 3 months of the study. Participants in the IPS Plus Abstinence-Contingent Wage Supplements group will get abstinence-contingent incentives for engaging in IPS supported employment and for obtaining and maintaining competitive employment. These incentives should increase attendance in the Therapeutic Workplace, development of job skills, employment, abstinence from heroin and cocaine, reduction in drug-related HIV risk behaviors. The earnings and payments could also have the benefit of providing a means of purchasing things that the family would not otherwise be able to afford.

The GMA component of the study is not expected to impart any direct benefit to participants.

Benefits to others. The study will evaluate the effectiveness, cost-effectiveness, and cost-benefit of IPS Plus Abstinence-Contingent Wage Supplements in increasing employment and promoting long-term cocaine abstinence. This novel intervention could be an effective and economically sound means of promoting long-term cocaine abstinence and employment in injection drug users, a population at considerable risk for a range of adverse outcomes including HIV because of their poverty, unemployment and continued injection drug use. If participants complete the job training and use IPS supported employment services, they could become employed which could reduce their need for government services. If employed, they could also contribute to the overall tax revenue generated in their community. If the job skills training and employment program increases the employment of participants, it could reduce their poverty and reduce transmission of poverty to their children. If the intervention is effective in promoting abstinence from cocaine and opiates, it could reduce injection drug use and drug-related HIV risk behaviors. This could reduce the risk of transmitting HIV infection in the community.

The GMA component of the study will address important questions raised by previous findings at the NIDA IRP (Epstein and Preston, 2012). The implication of those findings was that work might cause reductions in stress and drug craving during treatment for addiction. But before drawing treatment recommendations or policy recommendations from that finding, we need corroborative information collected under more controlled conditions. This Therapeutic Workplace study will provide that. The result should be more reliable recommendations.

Risk/Benefit Ratio. Overall, there are limited risks associated with this protocol above normal daily living. There are considerable potential benefits to the participants in this study, to people living with the participants, and to the community at large. Overall, the risk/benefit ratio appears highly favorable.

10. Payment and Remuneration

All incentives in this study will be provided by giving participants reloadable credits and adding incentives to the card when earned. Restrictions can be placed on these cards to restrict where they can be used to make purchases. We have been using these reloadable credit cards in our ongoing research and they have proved attractive to participants and convenient for staff to manage.

Phase 1 Training Incentives. All participants will be invited to attend the Therapeutic Workplace for 4 hrs every weekday for about 3 months (12 weeks), where they can earn about \$10/hr for participating in our job skills or health education training program.

Some participants may get jobs in the community before their participation in the therapeutic workplace ends (i.e., before Phase 1 ends) and may have to stop attending our workplace to maintain their outside employment. Thus, we may offer wage supplements to participants who get jobs during Phase 1. Under the wage supplement procedure, participants would be able to earn a wage supplement for all hours that they work in a community job (up to our current maximum of 20 hours per week) as long as they continue to meet their drug abstinence requirements. The amount of the wage supplements will be equivalent to the current base pay hourly wage that participants can earn for working in the workplace. In total, participants will be able to earn \$2,400 in Phase 1 for training in the workplace and/or for wage subsidies. The amounts will vary depending on each participant's productivity and the number of hours worked.

Phase 2 Abstinence-Contingent Wage Supplements. Participants in the Abstinence-Contingent Wage Supplement group will be able to earn wage supplements of up to \$8 per hour for up to 40 hours per week for 52 weeks. In total, participants in the Abstinence-Contingent Wage Supplement group will be able to earn up to \$16,640 in wage supplements.

Participant payment for assessments. Assessments will be conducted for all participants at intake to determine eligibility and characterize the population, immediately prior to random assignment, periodically throughout the 3-month abstinence initiation period, every 30 days throughout the 12-month intervention evaluation period after random assignment, and then at 3, 6, 9 and 12 months after the end of the intervention evaluation period. Participants will be paid \$30 for the intake and pre-random assignment assessments, \$30 for each monthly assessment during the 3-month abstinence initiation period and the 12-month intervention evaluation period, and \$50 for the each assessment conducted 3, 6, 9 and 12 months after the end of the intervention evaluation period. In total, participants will be able to earn up to \$710 for completing the assessments in this study.

Participant referral fees. As in our previous studies, participants will have the optional opportunity to earn incentives for referring people who are interested in the study. If a referral attends the initial

screening appointment and completes the necessary assessments, the participant who referred the person will receive up to \$20. If a referred person enrolls in the main study, the participant who referred the person will receive up to \$40 for making the referral.

GMA-related payments. Participants can earn:

- \$ 5 / day (\$2.50 for each drug/urine day) if urine is negative for cocaine and heroin/opioids and no self-reported use for either drug on smartphone OR if urine is positive for either cocaine or heroin/opioids and there is self-reported use (on smartphone) of the drug for which the participant tested positive (i.e., if urine positive for cocaine, must have self-reported cocaine use, etc.). Payment is only made for corresponding urines and smartphone self-reports; no payment is made for non-corresponding data. When a urine sample is missed or no data is able to be retrieved from the smartphone and there is no evidence for a malfunctioning smartphone is found, there will be no payment for that day.
- \$30 / week will given if at least 82% of random prompts are answered during that week (regardless of drug-use entries)
- \$5 / week will given if the participant presents the charged phone at all study visits during the week
- While credit is accumulated for each urine/smartphone correspondence, which occurs 3x weekly, participants may only be paid 1 time per week.
- The participant will receive \$200 for return of the smartphone.

Participants can earn up to \$50/week for about 12 weeks for compliance with GMA entries and carrying and charging the smartphone, and \$200 for returning the smartphone for a total maximum remuneration of \$800. Airtime on the smartphone for the 12-week period has a value of approximately \$120. Payment will be made in cash.

Quality of life monitoring payments. Participants can earn up to \$10 per week for answering questions in the Delight Me application. Each week, participants can earn \$5 if they answer the majority of daily-administered questions and \$5 if they answer a majority of the weekly-administered questions. Payment will be made in cash.

11. Costs

There will be no costs to participants for any services or treatment provided in this study. All procedures in the study will be paid for out of grant funds.

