Wednesdays, and Fridays). The immediate work group will be invited to work in the workplace 4 hrs every weekday, where they can earn about \$10/hr for participating in our job skills training program. This initial period will last for 3 weeks. After the initial three weeks, all participants will be invited to work in the workplace for 4 hours every weekday. GMA data (see below) will be used to compare participants' mood and behavior during weeks that they are at work (Immediate Work group) to weeks where they are not at work (Delayed Work group).

Abstinence initiation. After the 5 week induction period, participants will be required to provide urine samples negative for opiates and cocaine to maintain maximum pay. To allow us to evaluate the effectiveness of the contingencies for opiate and cocaine abstinence in promoting abstinence, we will implement the requirement for opiate-negative and cocaine-negative urine samples after varying durations in the induction period. At the end of Phase 1, participants will be randomly assigned to the study groups.

Vacation days. On quasi-randomly selected work days, all participants will have a paid "vacation" day. During a vacation day, participants will be able to earn their typical pay, but they will not have to attend the workplace and work to earn it. This will enable us to assess how unexpected free time affects mood and behavior. We have used similar paid vacation days to maintain participants' pay during actual holidays, weather emergencies and other workplace closings. GMA data (see below) will be used to compare participants' mood and behavior on days that they are at work (regular work days) to days where they are not at work (vacation days)

Geographical Momentary Assessment (GMA). The GMA-related procedures will occur for 12 weeks of the first 3 months of Phase 1. One week after signing informed consent, all participants will be issued a smartphone for GMA. The one-week delay is to help ensure that smartphones are issued only to participants who intend to return.

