For ambulatory assessment of mood and behavior, questions will be programmed as an application on the smartphone. The smartphone's integrated GPS unit will collect geographical location data at 5-minute intervals. The app will be password protected on the phone; questionnaire responses and GPS data will be encrypted and transmitted from the smartphone to a secure NIH server. Participants will be able to use the phones for their personal use. In addition to GMA data for location and self-report, we will record the amount of time and frequency of phone use (voice and text messaging), but no text or voice content will be recorded.

When the smartphones are issued, participants will be shown how to use and charge them, and will be asked to carry them at all times. At each visit to the Therapeutic Workplace, their possession and the charge level of the phone will be recorded. The smartphones will be activated for airtime for collection of location (GPS) and real-time self-report data and for personal use as a mobile phone by the participant. The visit for initial training on the smartphone is expected to take 30 minutes, during which participants will also complete the Perceived Neighborhood Scale (Martinez et al., 2002), which is a questionnaire that will help us understand their interactions with their home environments.

Participants will carry the smartphones for up to 12 weeks, during which they will make four types of entries. Each entry takes 3-5 minutes. The list of questions presented at each type of entry is provided in the Supplemental Documents section of the e-IRB application.

- Random-prompt entries: Participants will be prompted three times per day by the app, at random times during their waking hours. They will report their mood, stress level, environmental setting, activities, and degree of craving. Hours for prompting will be adjustable in accordance with the participant's typical sleep/wake schedule; participants will also be able to turn off random prompting in settings where it would be disruptive (such as driving, showering, or religious services).
- Drug-use entries: Participants will initiate an entry whenever they use cocaine, heroin, another opioid or stimulant outside of a medical context.
- Drug-craving entries: Participants will initiate an entry whenever they crave cocaine, heroin or another opioid, without using.

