Review and expungement of criminal record. Criminal records are a major barrier to competitive employment in adults with a history of illicit drug use. To help participants prepare for competitive employment, we may collaborate with community partners (e.g., Maryland Legal Aid) who offer free legal assistance to participants in Phases 1 and 2. This assistance typically consists of determining eligibility for expungement, processing petitions for expungement of criminal records, and other free services approved by the legal team. Participants are notified by research staff that legal assistance is available, and that participation is voluntary. We may collect data to describe and evaluate the expungement process so we may better understand legal barriers to employment in adults with a history of illicit drug use. The data we would collect are the types of offenses participants have on their public records (i.e., records available to potential future employers), the number of convictions on record, which records are eligible or ineligible for expungement, whether petitions for expungement are filed by the legal team, whether petitions for expungement are granted or require a hearing, and how long it takes for participants to have their records expunged. We may publish an article to describe the expungement process and de-identified data of our participants. All data that we collect and publish on the criminal histories of our participants will be data that are publicly available.

Random Assignment

Participants (N = 120) will be randomly assigned to an IPS Only (Control) or IPS Plus Abstinence-Contingent Wage Supplements group. A computerized urn randomization procedure (Wei & Lachin, 1988) will be used to balance groups on three baseline characteristics that may influence outcome: (1) percentage of the three monthly urine samples collected prior to random assignment that are positive for cocaine (\geq rolling median, Y/N); (2) percentage of the three monthly urine samples collected prior to random assignment that are positive for opiates (\geq rolling median, Y/N); and (3) completed high school or obtained a GED (Yes/No). Participants will be stratified by cocaine and opiate use because drug use at random assignment should predict abstinence from opiates and cocaine and possibly employment during the intervention evaluation period. High school completion or GED should be associated with employment

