Analyses for the secondary GMA aim. Most of these analyses will be done by [name] group. Like the other repeated measures, the GMA data will be analyzed with longitudinal regression models. [name] group uses mixed models (Proc Mixed and Proc Glimmix in SAS 9.4) to handle within-person correlation and missing data. Tests will be two-sided and p-values <.05 will be considered significant. The main comparisons of interest will be: (a) Between-group comparisons of mood, craving, stress, and other GMA measures during weeks 2-3, when participants have been randomized to immediate versus the delayed work condition. (Waitlist participants who have other employment during weeks 2-3 will be excluded from most of these analyses.) (b) Within-person assessment of changes in those variables in the delayed work group, comparing weeks 2-3 to weeks 5-13. (c) Contrasts in all participants between unannounced vacation days and the corresponding weekdays from a week with no vacation. For comparisons a, b, and c, effect sizes are expected to be fairly large, because work accounted for 20-50% of the variance in mood and craving in a EMA prior study at the NIDA IRP (Epstein and Preston, 2012). We will also assess (d) between-group and within-person differences in GPS-assessed activity space during working and nonworking periods. We have no prior data on that question; those analyses will be exploratory.

Economic Analyses

Our economic evaluation will be done from the provider perspective.

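### If vacation dates are shared by everyone in Phase 1, the vacation-versus-work contrast in the GMA analysis needs a calendar-date effect, and the plan names only within-person correlation

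*Combined protocol and SAP*

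**What the plan says.** Section 4, Vacation days: "On quasi-randomly selected work days, all participants will have a paid" vacation day, on which they keep their usual pay without attending. The purpose is to learn how unexpected free time affects mood and behavior. The same paragraph says that similar paid days were used before to maintain pay "during actual holidays, weather emergencies and other workplace closings". It does not say how many vacation days there are, by what rule they are selected, or whether a selected date applies to everyone or to one participant.

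Section 7c, Analyses for the secondary GMA aim, comparison (c): "Contrasts in all participants between unannounced vacation days and the corresponding weekdays from a week with no vacation". The models are mixed models, used "to handle within-person correlation and missing data", and "Tests will be two-sided and p-values <.05 will be considered significant". A calendar-date term is neither mentioned nor excluded.

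On data volume, Section 4 says "Participants will be prompted three times per day by the app", for up to 12 weeks. The plan gives no sample size, power or standard error for comparison (c).

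**The concern.** In the Vacation days sentence, the things selected are work days and the recipients are all participants. On that reading, the unit assigned to vacation is the date. Whatever else is particular to that date, such as weather or a local event, reaches everyone who answers prompts on it. A model whose only source of dependence is the person then counts each participant's vacation day as separate evidence about free time, although part of it is one shared observation of the date.

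Matching on weekday removes ordinary Monday-versus-Friday differences. It does not remove what is peculiar to one particular Monday.

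At stake is the interpretation of comparison (c). It is the only listed contrast that takes work away from all participants on particular days: (a) is between the immediate and delayed work groups, and (b) uses the delayed work group alone. Date-to-date noise could be reported as an effect of unexpected free time.

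**Working it through.** The plan gives no figure for this contrast, so there is nothing to reproduce. The check asks how far the test could be off if dates are shared.

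**Inputs from the plan:** two-sided 5% test; same-weekday comparison; within-person correlation as the only named dependence; 120 participants randomized to the main groups (the GMA number is not stated separately).

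**Assumptions, not in the plan:** m, the number of participants sharing a date, is 10-20; ρ, the share of person-day residual variance common to the date, is 0.02-0.05.

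**Formulas:**
- Design effect: DE = 1 + (m − 1)ρ
- True SE divided by model SE: √DE
- Actual type I error: 2 × [1 − Φ(1.96/√DE)]

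**Ends of the range:**
- m = 10, ρ = 0.02: DE = 1 + 9 × 0.02 = 1.18; √DE = 1.09; the model SE is 1 − 1/1.09 ≈ 8% too small; type I error 7.1%.
- m = 20, ρ = 0.05: DE = 1 + 19 × 0.05 = 1.95; √DE = 1.40; the model SE is about 28% too small; type I error 16.0%.

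**Simulation:** 120 people, 3 vacation days each (assumed), each paired with the same weekday in the following week, no true effect, within-person differences tested at two-sided 5% with no date effect in the analysis, 4,000 runs per setting.

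| m | ρ | Formula, shared dates | Simulated, shared dates | Simulated, individual dates |
|---|---|---|---|---|
| 10 | 0.02 | 7.1% | 6.8% | 4.9% |
| 10 | 0.05 | 10.4% | 10.2% | 5.5% |
| 20 | 0.02 | 9.5% | 8.7% | 5.5% |
| 20 | 0.05 | 16.0% | 16.9% | 6.0% |

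With ρ = 0 every simulated setting gave 4.5-5.8%, so the excess comes from the date effect. Outside the assumed range, at m = 40 and ρ = 0.10, the simulated error was 38.2% with shared dates and 9.3% with individual dates. Individual dates therefore remove most of the problem, but not all of it when many people are present and dates matter a good deal.

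**Is 10-20 per date plausible?** The relevant m is the number in Phase 1 at one time, not 120. If 120 people accrue evenly and each is followed for 12 weeks, m = 10 implies accrual over 120 × 12/10 = 144 weeks and m = 20 over 72 weeks. Accrual over four years (208 weeks) would give m = 120 × 12/208 ≈ 6.9 and a type I error of about 6.4-8.5% at the same values of ρ.

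**The case against.** The strongest reply is that shared dates are an inference. The sentence also fits each participant receiving vacation on selected days of their own schedule, and the holidays and weather closings describe earlier practice, not this trial's schedule. A common date also sits awkwardly with delayed work participants in their first three weeks, who have only a brief sign-in to be excused from. This stands as a limit: shared dates are the more natural reading, not a certain one.

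Second, the phrase about within-person correlation is a one-line reason for using mixed models, not a list of random effects, so a date effect is not excluded. That is correct. Still, a plan that names one source of dependence and leaves out another gives the analyst no instruction to include it.

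Third, the size is assumed throughout. Slow accrual and the GMA drop rules would lower m; Phase 1 starters who were never randomized would raise it. The plan also expects fairly large effects, and if these appear, a standard error 8-28% too small would seldom reverse a conclusion. Both points stand, and both bear on how much the issue matters rather than on whether the term belongs in the model.

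Fourth, rescheduling is probably moot. The document is dated March 2022, and the COVID-19 procedures say the remaining assessments need no in-person contact, so Phase 1 attendance may be over. That is why the main remedy lies in the analysis.

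**Conclusion.** The point holds conditionally. The plan leaves open whether vacation dates are common or individual, and it does not say how date-level correlation is handled in comparison (c). If dates are shared, several people share each one, and mood or craving has any date-level correlation, the standard errors would be too small. Under the assumed 10-20 people per date and correlation of 0.02-0.05, the type I error is about 7-16% against a nominal 5%; with individual dates it stays near 5-6%.

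A reader might go further and infer that the plan definitely gives everyone the same dates, that the reported standard errors will certainly be wrong, or that staff are free to pick the dates. The documents support none of these. The schedule is not stated, no date correlation or number per date is given, and nothing says who selects the days or how; quasi-random selection could equally mean constrained random selection.

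The consequence is confined to one comparison within a secondary aim. The primary outcomes, their GEE analysis and N = 120 are untouched. This is an inexpensive improvement rather than a serious defect.

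**What to change.** In Section 7c, add to comparison (c) a random effect for calendar date, crossed with participant, and use small-sample degrees of freedom (for example Kenward-Roger). Vacation dates may be few, and a date variance estimated from few dates is imprecise, so report how many distinct vacation dates contribute.

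In Section 4, Vacation days, state whether dates were common or individual, how many there were, and the rule used to select them. If any vacation days are still to be scheduled, draw them by computer separately for each participant, balanced over weekday and Phase 1 week.

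The cost is one model term in the mixed-model framework already planned, and a few sentences of text. Intervals become somewhat wider. If dates were individual the term does no harm. If they were shared, the extra width (a factor of 1.09-1.40 over the assumed range) is uncertainty that the person-only model would have left out.

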4. Study Procedures

Procedures for COVID-19

We will complete the remaining assessments without any in person contact. Interviews will be conducted over the phone and when possible we will obtain urine sample results from each participant's clinic. To do that, participants can ask their clinic to send us their urinalysis results. If needed, we will mail a re-loadable credit card to participants.

Recruitment Procedures

Identifying, Screening and Consenting Participants

Participants will be recruited from methadone and buprenorphine programs in Baltimore using procedures that we have used in prior evaluations of the Therapeutic Workplace (Donlin et al., 2008; [name] et al., 2007). First, we will inform staff at methadone and buprenorphine treatment programs in Baltimore about the study and encourage them to refer potential participants to us. Second, we will post flyers and distribute business cards and information sheets with our toll-free number in each of these programs. Copies of the proposed flyer, business card and information sheets are enclosed with this application. Third, we will visit programs and recruit for the study onsite at each program. Fourth, as in our previous studies, participants will have the optional opportunity to earn incentives for referring people who are interested in the study. If a referral attends the initial screening appointment and completes the necessary assessments, the participant who referred the person will receive up to \$20. If a referred person enrolls in the main study, the participant who referred the person will receive up to \$40 for making the referral.

Experimental Design and Groups

Phase 1 Abstinence Initiation and Job Skills Training

All participants will be invited to attend Phase 1 of the Therapeutic Workplace for about 3 months where they can earn up to about \$40 every weekday and provide urine samples every Monday, Wednesday and Friday. To engage participants, both groups will be allowed to earn wages independent of their urinalysis results for the first 5 weeks.

Delayed Work vs. Immediate Work group. To assess the potential value of working in the workplace every weekday, upon enrollment in the study participants will be randomly assigned to a delayed work group or to an immediate work group. The delayed work participants will be paid a daily wage of \$40 for coming to the workplace to sign in and provide a urine sample (on Mondays,

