
To gain verified and objective records of employment, we may get an objective measure of each participant's employment history by getting each participant's earnings history using federal Form SSA-7050-F4 (10-2016) UF, REQUEST FOR SOCIAL SECURITY EARNINGS INFORMATION. Participants and research staff will complete this form and have the participant's earnings history sent to our research unit. Our research unit will pay for the costs of this service. We may request these documents one or more times. We will take the following steps to protect this sensitive information in our study databases (see also Section 8b): (1) when storing a completed form, we will redact name, date of birth, and social security number from the written document and label the document with an ID number; (2) keep paper copies in a locked file cabinet in a locked office and never keep documents out while unattended by research staff; (3) only enter relevant information into the database (i.e., information about when participants worked, how much they earned, and what type of employment they had); and (4) maintain a confidentiality certificate from the NIH. The risks associated with collecting this information are explained on the consent form.

a. Study duration and number of study visits required of research participants.

Participants will be invited to attend Phase 1 of the therapeutic workplace every weekday for 3 months. Participants in the immediate-work group will attend for 4 hours every weekday. Participants in the delayed work group will be asked to come to the workplace every day for a brief visit (30 minutes or less) to complete study measures for the first 3 weeks and then for the full 4 hours for the remainder of the 3 month period of Phase 1. All participants that report to be assessed at the end of Phase 1 will be randomly assigned to the primary study groups and offered Individual Placement and Support for 1 year. The IPS intervention is designed to promote employment in competitive community workplaces. All participants will be invited to participate in an intake assessment to determine eligibility and characterize the population. Outcome assessments will be conducted every 30 days throughout the 3-month abstinence initiation period, every 30 days throughout the 12-month intervention evaluation period after random assignment, and then at 3, 6, 9 and 12 months after the end of the intervention evaluation period.

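### Work timing is randomised a week before smartphones are issued, so the weeks 2–3 between-group GMA contrast omits anyone lost in week 1, after randomisation

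*Combined protocol and SAP*

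**What the plan says.** The trial randomises twice. The first randomisation is in section 4 (Delayed Work vs. Immediate Work group): "upon enrollment in the study participants will be randomly assigned to a delayed work group or to an immediate work group". The delayed group receives a daily 40 dollars "for coming to the workplace to sign in and provide a urine sample", and section 4.a puts each visit at half an hour at most. For the other arm, "The immediate work group will be invited to work in the workplace 4 hrs every weekday", at about 10 dollars per hour. On how long the arms differ: "This initial period will last for 3 weeks".

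Section 4 (Geographical Momentary Assessment) has phones given to all participants one week after consent, and gives the reason for waiting: "The one-week delay is to help ensure that smartphones are issued only to participants who intend to return".

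Section 7.c (Analyses for the secondary GMA aim) lists as comparison (a) the between-group differences in mood, craving, stress and other GMA measures "during weeks 2-3, when participants have been randomized to immediate versus the delayed work condition". Comparison (d) includes between-group differences in activity space. Mixed models are named for within-person correlation and missing data. Section 9 says of the earlier observational finding that "we need corroborative information collected under more controlled conditions. This Therapeutic Workplace study will provide that".

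**The concern.** Randomisation protects a comparison among everyone who was randomised. Here a week passes between assignment and the first GMA measurement, and in that week one arm is asked to work four hours a day while the other signs in briefly. The wait is meant to screen out people who will not come back. A screen placed before randomisation would do no harm. Placed after it, with the arms already treated differently, it can remove different kinds of people from each arm.

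The GMA objective in section 2 asks whether work is a respite or a stressor. A person's reason for not returning in week 1 may be related to that outcome. Comparison (a) is also the only planned comparison of mood, craving and stress between people randomised to work and people randomised not to work.

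**Working it through.** **1. Timeline.** The plan gives about 252 prompts over 12 weeks at three a day: 3 × 7 × 12 = 252, which reproduces its figure. Comparison (b) runs to week 13, and weeks 2 to 13 are 13 − 2 + 1 = 12 weeks. Phones therefore run from week 2. Week 1 has no GMA data and lies inside the three weeks in which the arms differ. One gap remains: the phone clock starts at consent and the assignment is made at enrolment, and the interval between them is not stated. The week numbering implies that week 1 follows randomisation.

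**2. What the arms face in week 1.** Daily pay is about 40 dollars in both. Full attendance is 5 × 4 = 20 hours a week in the immediate arm and at most 5 × 0.5 = 2.5 hours in the delayed arm. That is 40 / 4 = 10 dollars per hour against at least 40 / 0.5 = 80. Different return rates are plausible, but the documents report none.

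**3. What the analysis plan does about it.**
- Mixed models can use partial records. A person never given a phone has no record.
- The intent-to-treat statement is in the Main analysis paragraph of section 7.c and is not repeated for GMA.
- The Missing data paragraph compares participants with and without missing values by covariates and treatment assignment, but is not extended to GMA or to the work-timing arms.
- Waitlist participants (apparently the delayed arm) with other jobs in weeks 2–3 are excluded from most of these analyses. This is a second selection after randomisation, stated for one arm only.

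**4. Possible size (all inputs assumed).** If one arm loses an excess fraction p whose scores would differ by d SD from those who stay, the full-arm mean is the stayers' mean − p × d, so bias = p × d:
- p = 10%, d = 0.5: 0.05 SD
- p = 10%, d = 1.0: 0.10 SD
- p = 20%, d = 1.0: 0.20 SD

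A second model allows loss in both arms. The outcome correlates r with a normal propensity to return, and each arm loses its lowest fraction a, with cut-off c. Then bias = r_I φ(c_I)/(1 − a_I) − r_D φ(c_D)/(1 − a_D), with I the immediate and D the delayed arm. For losses of 20% and 10% the ratios are 0.280/0.80 = 0.350 and 0.1755/0.90 = 0.195, a difference of 0.155. This gives 0.03 SD at r = 0.2 and 0.08 SD at r = 0.5. The rejection rate is for a two-sided 5% z test with no true effect, one value per person and 60 per arm before loss. The 60 is illustrative: the plan's 120 belongs to the later IPS randomisation, and the number randomised to work timing is not stated.

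| Loss, immediate / delayed | r | Bias (SD) | Rejection under no effect |
|---|---|---|---|
| Equal, same selection | any | 0 | 5.0% |
| 20% / 10% | 0.2 to 0.5 | 0.03 to 0.08 | 5.3% to 6.8% |
| 30% / 5% | 0.2 to 0.5 | 0.08 to 0.19 | 6.7% to 15.9% |
| 20% / 20% | 0.4 / 0 | 0.14 | 10.5% |

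Swapping the arms' inputs reverses the sign. The last row shows that equal loss is no protection if different kinds of people leave each arm.

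**5. Scope.** Comparison (b) is within person in the delayed arm, and (c) contrasts vacation days with ordinary days in all participants. Imbalance between arms does not distort either, though both describe phone recipients only. The IPS comparison has its own randomisation at the end of Phase 1.

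**The case against.** The plan says that all participants will be issued a phone, and the screening is a stated purpose and not an eligibility rule. Participants are invited to work, and the only removal criterion in section 4.e is a threat to safety. Someone who dislikes the work could skip it, stay enrolled and collect a phone. Both arms can earn similar daily pay whatever their urine results in the first five weeks, both are offered the phone payments in section 10, and everyone has expressed interest in employment. This stands: nothing makes phone issue conditional on tolerating work, and differential loss is a possibility and not a fact. It does not remove the point, because a person who does not come back cannot be given a phone.

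A reader might infer that the bias favours the respite hypothesis, because people who find work stressful would leave the immediate arm. The documents do not support a direction. Participants who wanted training at once and were assigned to wait could leave the delayed arm.

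A reader might also infer that the selection cannot be adjusted for. That is too strong. There is no GMA measure from before work starts, but every participant has an intake assessment and urine samples are scheduled from the start of Phase 1. Comparison of recipients with non-recipients, weighting and bounds are all possible.

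Finally, the plan expects large effects, with work explaining 20–50% of variance. Read as a balanced two-group contrast, d = 2√(R²/(1 − R²)), which is 2√(0.20/0.80) = 1.0 and 2√(0.50/0.50) = 2.0. A bias of 0.20 SD is then at most 20% of the smallest expected effect. This limits the damage if such effects appear, but it rests on variance shares from an earlier study and does not help if the true effect is small.

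**Conclusion.** The point holds for comparison (a) and for the between-group part of (d) so far as it uses weeks 2–3. Both exclude anyone lost in week 1 after randomisation, and the plan neither recovers these people nor acknowledges their absence. Bias is possible, but its direction and size are unknown. It is nil if loss and selection match across arms, and about 0.05 to 0.20 SD under the simple assumptions above (0.03 to 0.19 SD in the tabulated two-arm cases). All of these rest on assumed loss rates.

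A reader might conclude that the claim in section 9 of more controlled evidence fails altogether. The documents do not support that. The claim is made for the whole GMA component, and comparisons (b) and (c) are untouched by imbalance between arms. This is a weakness in one secondary between-group contrast. It should be corrected, or the contrast described differently, and it has no bearing on the primary outcomes.

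**What to change.** Make week 1 a common run-in with the brief sign-in and urine visits for everyone, and randomise work timing at the phone-issue visit. The wait then still saves phones, everyone randomised is present when phones are handed out, and weeks 2–3 remain the comparison window.

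The cost is that the immediate arm starts work a week later, and weeks 2–3 become its first two weeks of work instead of its second and third. The delayed period after randomisation either shortens to two weeks (weeks 2–3) or is extended by one (through week 4). Either choice leaves the windows of comparison (b) as they are. No extra visits or staff are needed.

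This may come too late: the document is dated March 2022, and its COVID-19 text speaks of completing remaining assessments without personal contact. If enrolment under the current order is complete:
- report week-1 return and phone issue by assigned arm;
- compare recipients with non-recipients on intake data, by arm;
- add a weighted or bounded sensitivity analysis for (a) and for the affected part of (d);
- describe (a) as a comparison among phone recipients and not as a fully randomised one.

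These steps need only records the study should already hold.
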